This study is in patients with neuropathic pain, and will culminate in a quantitative description of interactions between activators of descending noradrenergic activity, norepinephrine transporter inhibitors, and cholinesterase inhibitors to exploit this unique plasticity of analgesia in chronic pain states. We focus not only on mechanistic hypotheses in the laboratory studies, but also on practical applications, using clinically approved drugs, including gabapentin (Neurontin®) to activate noradrenergic activity, duloxetine (Cymbalta®) to inhibit the norepinephrine transporter, and donepezil (Aricept®), approved for the treatment of Alzheimer's dementia, but not previously tested to treat neuropathic pain, to inhibit cholinesterase. Each of these drugs may act by mechanisms in addition to those involved in descending noradrenergic inhibition, but we hypothesize that the therapeutic strength of their combination relies heavily on this cascade engendered by noradrenergic sprouting and altered α 2-adrenoceptor function. The proposed studies will provide critical tests of this hypothesis and critical information to guide more effective clinical therapy of neuropathic pain.

Protocol

Inclusion Criteria:

A total of sixty-six patients with diabetic neuropathic pain will be recruited from the Department of Neurology at Wake Forest University School of Medicine, surrounding Piedmont Triad community and we will also have a second site at the Cleveland Clinic Foundation in Cleveland Ohio. Patients with predominant neuropathic pain following back surgery will also be enrolled. Approximately 46

Version VI February 10, 2009 Page 2 of 11 subjects will be enrolled at WFUHS and 20 will be enrolled from the Pain Clinic at the Cleveland Clinic. Wake Forest University Health Sciences will be the coordinating center. [name], will be the PI for the Cleveland Clinic site. Subjects from the Cleveland Clinic will follow the same protocol as the WFUHS subjects.

1. Diagnosis of diabetic neuropathy

2. Age 18-80

3. Willing to temporarily discontinue gabapentin or monoamine reuptake inhibitors upon entry into the study

Subjects will be able to continue their other prescribed medications maintaining a stable dose.

4. Diagnosis of failed back syndrome.

Exclusion Criteria:

- 1. Pregnant women or women of child-bearing potential not willing to practice a reliable form of birth control as specified in the informed consent

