	Visit		Visit						Visit						Visit		Visit
	1		2						3						4		5
Informed	Х																
Consent																	
Urine	Х																
Pregnancy Test																	
Pain	Х																
Questionnaires																	
Physical Exam	Х																
PDA	Х																
Instructions																	
PDA Download			Х						Х						Х		Х
Randomization			Х														
Blinded Study Med			Х	Х	Х	Х	Х	Х	Х	Х	Х	Х	Х	Х	Х		
Gabapentin									Х	Х	Х	Х	Х	Х	Х	Х	Х

Primary Outcome Measures:

Pain intensity measurements will be recorded twice daily, in the a.m. and p.m. using McGill short form pain questionnaire displayed on the personal digital assistant (PDA). The SF-MPQ is comprised of 15 descriptors (11 sensory; 4 affective) with an intensity scale from 0-3 (3 being the most severe), present pain intensity (PPI), and Visual Analog Pain Scale (VAS). The VAS will serve as the study's primary outcome measure.

Statistical Analyses:

All data will be analyzed using the most recent version of SPSS (SPSS Inc., Chicago, IL). Prior to performing analyses related to the aims and hypotheses, descriptive statistics will be computed to examine if assumptions needed for parametric analysis are met. Our previous studies of daily pain reports from neuropathic pain Version VI February 10, 2009 Page 6 of 11 patients (1) have indicated that such reports can be expected to be approximately normally distributed. If parametric assumptions are not met, standard transformations will be used to make the data more normal. An intent-to-treat analysis will be undertaken for all participants that receive at least one study dose (with last observation carried forward for drop-outs) with no attempts being made to impute missing data. A two-tailed probability value of .05 will be used for statistical significance criterion in all analyses.

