To examine differences in the primary outcome of twice-daily pain reports as a function of "medication group" and "study phase", a Linear Mixed Model will be used. Subjects will be treated as a random variable, with the average of the daily pain reports nested within subject. A first-order autoregressive error term will be used to account for the repeated measures within subjects. Although all observations will be used to specify the model, only the observations from the last week (the optimal therapeutic dose) of each study phase ("baseline", "study med", and "gabapentin") will be used to evaluate the hypothesis. In essence, this allows changes in the dependent variable of pain reports to be modeled by two ANCOVAs (controlling for baseline). Group (placebo, duloxetine, donepezil, and duloxetine + donepezil) differences in pain reports will be evaluated separately at end of treatment alone and at end of treatment with gabapentin portions of the study. A significant group effect will indicate that mean self-reported pain scores differed significantly by treatment arm assignment during that phase of the study._ If a main effect is found, post hoc analyses will be conducted to indicate the location of the differences and to index the degree of change exhibited by study group.

In addition to the primary analyses, we will examine pre-post changes in disability measures and psychometric measures, global assessments of change, and medication use. Each of these outcomes will be examined using General Linear Models (GLM), examining for differences in group either at one time period or as a function of study phase, as appropriate. Further, because the study design will result in a time-series of pain reports for each subject, we will fully utilize the available data by creating individualized interrupted time-series analysis models for each subject. Within each phase, increases in dose will be modeled as a gradual, permanent intervention. We will utilize ARIMA models (2) to account for the unique data structure that our design results

Version VI February 10, 2009 Page 7 of 11 (i.e., diurnal variation in AM and PM reports). These analyses will better elucidate the nature of individual differences in the medication responses and identify the dose-response function for each medication condition.

Statistical Power Considerations:

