For the proposed study all power calculations are based on the primary analysis of the primary outcome measure (daily pain reports). ANCOVA analyses were chosen to evaluate the primary outcome as they have repeatedly been shown to be the most powerful technique for these comparisons (3). Our previous diary studies examining novel agents on neuropathic pain (1) have demonstrated that high levels of visual analog pain reporting are common, M = 60.5, and that substantial variation is often observed, even within day-to-day reporting, SD = 14. Nevertheless, first-order autocorrelation among observations is often observed, r = .20. For the present study, we are preparing for a considerable placebo effect of 20%. Because of the novel nature of the agents being studied, we would like to detect differences as small as 5% between the active treatment and placebo groups (i.e., a 25% reduction in pain from baseline). Using Cohen's formulation for ANCOVA (6) (f = .25, r = .50 between phases) with adjustment (4) for the calculation of our repeated assessment of each study phase (7 observations contributed by each subject at each phase, first-order autocorrelation = .20), we estimate that an n = 15 for each medication group (15 x 4 = N = 60) will provide power = .80. It is of note that the proposed sample size indicates the number of participants that take at least one dose of the study drugs (i.e., recruitment will end when N = 60 participants have taken at least one dose of study medication). Further, the 16 week trial, with two observations per day provides a sufficient number of observations ($n \sim 224$ observations/subject) to incorporate the interrupted time-series analysis strategy for the secondary analyses (5).

Adverse Events/Side Effects:

Version VI February 10, 2009 Page 8 of 11 The most common side effects of duloxetine observed in diabetic peripheral neuropathy groups include but are not limited to nausea, excessive drowsiness, dizziness, constipation, dry mouth, excessive sweating, decreased appetite and weakness.

The most common side effects of gabapentin are dizziness, excessive drowsiness, peripheral edema, nausea, dry mouth, constipation and ataxia. Other side effects include tiredness, flu syndrome, double or blurred vision, shakiness, and abnormal thinking.

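### Between-arm estimates of primary VAS pain are planned only if the four-arm test is significant, so a null result carries no planned estimate and a positive one is filtered on significance

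*Combined protocol and SAP*

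**What the plan says.** The Statistical Analyses section fits a linear mixed model that amounts to two baseline-adjusted ANCOVAs, one at the end of treatment alone and one at the end of treatment with gabapentin. At each point, "Group (placebo, duloxetine, donepezil, and duloxetine + donepezil) differences in pain reports will be evaluated separately". The significance rule is: "A two-tailed probability value of .05 will be used for statistical significance criterion in all analyses". What follows the four-arm test is conditional: "If a main effect is found, post hoc analyses will be conducted to indicate the location of the differences and to index the degree". The only description of this index is in the closing words of that sentence: "index the degree of change exhibited by study group". The text does not say whether that change is measured against the arm's own baseline or against placebo.

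The other planned analyses carry no such condition. They are general linear models for disability, psychometric, global-change and medication-use outcomes, and a separate time-series model of pain for each subject. None is described as a between-arm estimate of the primary outcome.

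The background section says the study "will culminate in a quantitative description of interactions" among the drug classes. Statistical Power Considerations states both "we are preparing for a considerable placebo effect of 20" per cent and "we would like to detect differences as small as 5% between the active treatment and placebo groups".

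**The concern.** A rule that makes estimation wait for significance has two consequences. If the omnibus test is not significant, the plan calls for no active-versus-placebo difference and no interval, so the report need not say what size of effect the trial excludes. That sits badly with an aim of quantitative description. If the test is significant, the estimates come only from trials in which the arms happened to lie far apart, and they are biased away from zero. A later trial sized on such an estimate would be too small.

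The undefined index adds a third risk. If it were computed as change from baseline within an arm, it would contain the placebo response. This point is about estimation, not multiplicity.

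**Working it through.** **Inputs.** From Statistical Power Considerations: baseline mean 60.5, SD 14, r = .50 between phases, 7 observations per phase with autocorrelation .20, f = .25, 15 per arm (N = 60), power .80, placebo response 20%, target difference 5%. From Statistical Analyses: two-tailed .05.

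**Assumptions.** SD 14 is the SD of one report (the text is unclear); 5% is of the 60.5 baseline; allocation is equal; nothing is lost to dropout.

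**Step 1: reproduce the plan's power.** The omnibus F test has 3 and 60 − 4 − 1 = 55 df, with noncentrality λ = N f²/v, where v is the variance factor for the weekly mean. With v = (1 + 6 × .20)/7 = .314, λ = 60 × .0625/.314 = 11.93 and power is .81, with 15 per arm needed for .80. The stated figure is reproduced. The matching SD is 14 × √.314 = 7.85.

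**Step 2: the 5% difference.** .05 × 60.5 = 3.025 points. With all three active arms better than placebo by that amount, f = √(3/16) × 3.025/14 = .094. The table gives omnibus power at this f; how often the test is non-significant; the mean combination-versus-placebo benefit among simulated trials with omnibus p < .05; its ratio to 3.025; and the unconditional 95% half-width for one pair, t(.975, 55) × SD × √(2/15).

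| Variance assumption | v | SD | Power | No planned estimate | Mean estimate if significant | Ratio | Half-width |
|---|---|---|---|---|---|---|---|
| AR(1) mean of 7, × (1 − .50²) | .151 | 5.44 | .295 | 71% | 4.6 | 1.5 | 4.0 |
| .314 × (1 − .50²) | .236 | 6.80 | .198 | 80% | 5.3 | 1.8 | 5.0 |
| .314 (reproduces .80) | .314 | 7.85 | .157 | 84% | 5.8 | 1.9 | 5.7 |
| One observation, 1 − .50² | .75 | 12.12 | .091 | 91% | 7.2 | 2.4 | 8.9 |

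Without the filter, the mean estimate equals the true 3.0 points in every row.

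**Step 3: a more favourable pattern.** If the single drugs are 5% better and the combination 10% better (an assumed pattern), f = .153. Omnibus power is .37 at SD 7.85, .69 at 5.44 and .17 at 12.12, so no estimate follows in 63%, 31% and 83% of trials.

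**Step 4: the plan's f = .25.** With three equal active arms this needs .25/√(3/16) × 14 = 8.1 points, or 8.1/60.5 = 13% of baseline. At SD 7.85, power is .81, so no estimate follows in about 19% of trials. When the test is significant, the estimate averages 8.8 against 8.1, a ratio of 1.09.

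**Step 5: the index.** On the plan's figures, change from baseline is .25 × 60.5 = 15.1 points on active treatment and .20 × 60.5 = 12.1 on placebo. The treatment effect is 15.1 − 12.1 = 3.0, so a within-arm index would be five times the effect.

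**The case against.** Four objections deserve an answer.

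- **The likeliest result.** A reader might infer that the trial will most likely end without an estimate. That is so at the 5% difference but not at f = .25, where power is about .81. The gap between those two inputs is a sample-size question in its own right. The objection limits the claim. The rule can still fairly be tested at the difference the sponsor says it wants to detect, and even at f = .25 about one trial in five ends without a planned estimate.
- **The index.** A reader might infer that effects are to be indexed as change within each arm, placebo response included. The documents do not say so. The phrase is undefined, the same sentence provides for locating differences between groups, and the ANCOVAs compare groups. This is an ambiguity to close, not a stated error.
- **The size of the exaggeration.** Requiring the combination-placebo pair to be significant as well would give larger inflation, but the plan states no such second filter. Only the omnibus condition is counted here. At f = .25 its effect is slight.
- **No estimate at all.** The ungated secondary models and individual time-series models contribute to a quantitative description, and nothing forbids reporting adjusted means from a model already fitted. That is correct. What is missing is a planned between-arm estimate of the primary outcome; permission to report one is not a commitment to do so.

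**Conclusion.** The concern stands in a limited form. Between-arm estimation of primary VAS pain depends on a significant four-arm test, and no unconditional contrast or interval is planned. At the plan's 5% difference, the planned estimate is absent in about 71% to 91% of trials (84% at the SD that reproduces .80). When present, it averages 1.5 to 2.4 times the true 3.0 points. At f = .25 under the same reproducing assumption, the figures are about one trial in five and about 9%.

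These sizes rest on the listed assumptions and describe one phase; the same rule applies at both. That the estimate is conditional rests on none of them, since it is in the text. Placebo response entering the effect index is a risk from undefined wording only.

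**What to change.** In Statistical Analyses, keep the omnibus test as the significance test, but remove the condition for estimation. State that at the end of each phase (weeks 8 and 14) the baseline-adjusted mean difference in VAS pain, each active arm minus placebo, will be reported with its 95% confidence interval whatever the omnibus p-value. Given the interaction aim, the combination minus each single drug may be added; that is optional and separate from the defect. Define the degree-of-change index as the between-arm adjusted difference.

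The cost is analysis wording: the models are already planned, and no patients or visits are added. The small downside is that wide intervals become visible, with half-widths of about 4.0 to 8.9 points (5.7 at the SD that reproduces .80, without multiplicity adjustment). All are wider than the 3.0-point target, which is information a reader of a null result needs.

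### The effect size f = .25 behind N = 60 does not follow from the 5% target: on the plan's own inputs, power for three active arms each 5% better than placebo is about 20% to 30%, not 80%

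*Combined protocol and SAP*

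**What the plan says.** Statistical Power Considerations takes its planning values from earlier diary work: "high levels of visual analog pain reporting are common, M = 60.5" and "substantial variation is often observed, even within day-to-day reporting, SD = 14". It allows for a 20% placebo response and adds that "we would like to detect differences as small as 5% between the active treatment and placebo groups", spelled out there as a 25% reduction from baseline.

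The calculation itself is described as an ANCOVA with "f = .25, r = .50 between phases", adjusted for repeated assessment with "7 observations contributed by each subject at each phase, first-order autocorrelation = .20". The result: "we estimate that an n = 15 for each medication group (15 x 4 = N = 60) will provide power = .80".

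Statistical Analyses sets the test. Group differences among the four arms are assessed by baseline-adjusted ANCOVA, separately at the end of each treatment phase, and post hoc comparisons follow only if the group effect is found. On the error structure: "A first-order autoregressive error term will be used to account for the repeated measures within subjects". On alpha: "A two-tailed probability value of .05 will be used for statistical significance criterion in all analyses".

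The plan gives no four-arm pattern of means and no step that turns 5% into f = .25.

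**The concern.** Cohen's f is the standard deviation of the group means divided by the error SD, so it is fixed once the means and the SD are given. The plan gives a small difference and a large SD, then uses an f that looks too big for them.

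If so, the .80 describes a much larger effect than the one the trial says it wants to detect. Two consequences follow. The group test would usually miss a 5% benefit, and the post hoc comparisons that depend on it would not be made. A null result could also be read as evidence against a 5% benefit, because the plan claims good power for it.

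**Working it through.** **Inputs.** Mean 60.5, SD 14, r = .50, m = 7 observations per phase, correlation ρ = .20, n = 15 per arm and N = 60 (Statistical Power Considerations); alpha .05, four-group test with one baseline covariate (Statistical Analyses). Error df = 60 − 4 − 1 = 55.

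**Step 1: the plan's own figure.** Power is taken from the noncentral F distribution with (3, 55) df and noncentrality λ = N·f²/v, where v is the variance of a seven-observation mean relative to one observation.

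- Equal correlation: v = (1 + 6 × .20)/7 = .314.
- First-order autoregressive, AR(1): v = [7 + 2 Σ(7 − k)(.20)^k]/49, k = 1 to 6, which is 9.875/49 = .2015.

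With f = .25, N·f² = 60 × .0625 = 3.75.

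- Equal correlation: λ = 3.75/.314 = 11.9, power **.81**. This reproduces the stated .80.
- AR(1), the structure the plan names: λ = 3.75/.2015 = 18.6, power .95.

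So the .80 comes from f = .25 with the equal-correlation factor, and with no further reduction for r = .50. Applying r = .50 on top of f = .25 would give .91.

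**Step 2: the f that the 5% target implies.**

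- Difference: .05 × 60.5 = 3.025 points.
- Covariate-adjusted SD: 14 × √(1 − .50²) = 12.12.

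| Pattern of the four means (total spread 3.025) | SD of means | f |
|---|---|---|
| Three active arms equal, placebo different | 3.025 × √3/4 = 1.310 | .108 |
| Two arms against two (largest f) | 3.025/2 = 1.513 | .125 |
| Two extremes, two in the middle (smallest f) | 3.025/(2√2) = 1.070 | .088 |

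Read the other way, f = .25 with three equal active arms needs .25 × 12.12 × 4/√3 = 7.0 points, or 11.6% of baseline (6.1 to 8.6 points over the other patterns).

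**Step 3: power at N = 60 for the 5% target.**

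| Pattern | Equal correlation (.314) | AR(1) (.2015) |
|---|---|---|
| Three equal active arms | .20 | .29 |
| Largest f | .26 | .38 |
| Smallest f | .14 | .21 |
| One active arm against placebo, unadjusted, 55 df | .22 | .32 |

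A simulated ANCOVA for three equal active arms gave .19 and .30.

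**Step 4: what N = 60 can detect.** Power .80 with (3, 55) df needs f/√v = .442. For three equal active arms:

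- Equal correlation: 6.9 points, 11.5% of baseline.
- AR(1): 5.6 points, 9.2% of baseline.

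**Possible cause.** The two-group standardized difference is 3.025/12.12 = .2495. Entering that value as f would explain the .25. The plan does not say this, and the conclusion does not depend on it.

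**The case against.** **f = .25 may be on a different scale.** If f refers to the seven-observation mean under AR(1), 3.025 points gives .108/√.2015 = .241 for three equal active arms and .278 for two against two, so .25 is within reach. That is correct, but the averaging gain is then already inside f and may not be applied again. Power at N = 60 is .32. Likewise, if r = .50 is kept outside f, three equal arms give f = .094 and f = .25 needs 8.1 points (13.4% of baseline). That changes the label, not the power in Step 3.

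**Equal active arms is not the trial's hypothesis.** The protocol expects a strong positive interaction, and 5% is put forward as a minimum. A better combination does raise the power of the group test. As illustrations not in the plan, single drugs at 5% with the combination at 10% give f = .176 and power .48 to .69; with the combination at 14%, f = .252 and power .81 to .95. But the plan states no such pattern, and none of it moves the .22 to .32 for a 5% difference between one drug and placebo.

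**Other readings of the inputs.** Pain is recorded twice daily, so a week could supply 14 readings; three equal arms then give .24 to .54, at the top slightly better than even. The power section specifies seven. Reading 5% as 5 points gives .49 to .70, but the text defines it relative to baseline. Counting all 66 planned patients gives .22 to .32. If SD 14 is only within-patient variation, power is lower than shown.

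**The formula may be in the cited sources.** The repeated-measures adjustment is referenced, and the reference may use the equal-correlation factor. The plan should still say so, because it names a first-order autocorrelation.

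What stands: the exact power depends on choices the plan leaves open. No reading of a 5% difference considered here reaches .80 without adding a larger combination effect.

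**Conclusion.** The concern holds. The stated power belongs to f = .25, and f = .25 does not come from a 5% difference. For three active arms each 3.025 points better than placebo, power at N = 60 is about .20 to .30 against the claimed .80; over any pattern with that total spread it is .14 to .38.

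This rests on 5% meaning 5% of the baseline mean, SD 14 being the total SD of a single observation, r = .50 applying between phase means, seven observations per phase and no loss of patients. The direction is secure. The exact figure varies with the correlation structure and the pattern of means, which is why both need to be written down.

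**What to change.** Keep N = 60 and rewrite the power paragraph. State the four assumed group means, derive f from them, name the within-phase correlation formula, and report the power or detectable difference that follows. Possible wording:

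> Assuming three equally effective active arms versus placebo, SD 14, r = .50 and seven observations per phase, n = 15 per group gives power .80 for a difference of about 6.9 VAS points (11.5% of baseline) under equal correlation .20, or about 5.6 points (9.2%) under AR(1) .20. Power for a 5% difference is about .20 to .30.

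The authors should keep whichever of the two structures they intend to plan on, and reconcile it with the autoregressive error term in Statistical Analyses. If a larger combination effect is assumed, it should be stated as such, with the power for a single drug against placebo given beside it.

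The cost is protocol wording and a less favourable detectable difference; no extra patients are needed. For scale only: holding both the 5% target and power .80 would take about 49 (AR(1)) to 75 (equal correlation) patients per arm, or 196 to 300 in total. The 5% target, N = 60 and power .80 cannot all stay.
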